2 STATISTICAL AND ANALYTICAL PROCEDURES

The statistical analysis and reporting will be based on all data from study TDR12857 and its extension study, LTS13769. The baseline value is defined as the last non missing value prior to first TDR12857 treatment, unless otherwise specified. The rebaseline values will be the last non-missing assessment before patients switch to 20 mg/kg dose for LTS-switch patients.

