Appendix B Visit windows

The analysis visits are assigned by comparing the distance between the calculated study day of each assessment (defined as time elapsed from the start of study drug in the TDR12857 study till the time of the assessment) with the listed target study days and the corresponding analysis windows of the applicable group of assessments, utilizing the general rules below:

1. If more than one non-missing values are assigned to the same analysis visit, then the assessment performed closest to the target study day will be used in the by-visit analysis.
2. Multiple values assessed on the same date will be averaged prior to being assigned an analysis visit.
3. If two assessments are assessed on different dates but equidistant from the target date, the values assessed on a later date will be used.
4. Use a combination of 2 & 3 in cases where there are multiple records equidistant from the target study day. For example, for a post-baseline visit, if there are 2 records, 7 days before the infusion and 3 records 7 days after the infusion, then take the 3 records after the infusion and average them for analysis value.

All visits in the applicable datasets will be used, including scheduled and unscheduled visits. (For change from TDR12857 baseline analyses, rebaseline visit and assessments performed after rebaseline will be handled in the same manner.) Note that baseline is defined as the latest available observation before the first infusion in the TDR12857.

Table 1 — Analysis windows for 6MWT, PFTs, ECG, hematology, and urinalysis:

VISIT (target study day*)	Analysis Visit	Analysis Visit Window (in study days*)
Baseline	Baseline	
Week 1@ in TDR (1)	Week 1	1 to 42 days
Week 13 in TDR (85)	Week 13	43 to 127 days
Week 25 in TDR (169)	Week 25	128 to 273 days/(1 st day of LTS – 1)**
Month 6 in LTS (365)	Week 52	(1 st day of LTS) to 456 days
Month 12 in LTS (547)	Week 78	457 to 638 days
Month 18 in LTS (730)	Week 104	639 to 821 days
Month 24 in LTS (912)	Week 130	822 to 1003 days
Month 30 in LTS (1095)	Week 156	1004 to 1186 days
Month 36 in LTS (1277)	Week 182	1187 to 1368 days
Month 42 in LTS (1460)	Week 208	1369 to 1551 days
Month 48 in LTS (1642)	Week 234	1552 to 1733 days
Month 54 in LTS (1825)	Week 260	1734 to 1916 days
Month 60 in LTS (2007)	Week 286	1917 to 2098 days
Month 66 in LTS (2190)	Week 312	2099 to 2281 days
Month 72 in LTS (2372)	Week 338	2282 to 2402 days

@ Week 1 visit only applies to ECG, hematology, and urinalysis.

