Week 11 in TDR (71)	Week 11	64 to 77 days
Week 13 in TDR (85)	Week 13	78 to 91 days
Week 15 in TDR (99)	Week 15	92 to 105 days
Week 17 in TDR (113)	Week 17	106 to 119 days
Week 19 in TDR (127)	Week 19	120 to 133 days
Week 21 in TDR (142)	Week 21	134 to 148 days
Week 23 in TDR (156)	Week 23	149 to 162 days
Week 25 in TDR (169)	Week 25	163 to 176 days/(1 st day of LTS – 1)**
Month 6 in LTS (365)	Week 52	(1 st day of LTS) to 548 days
Month 18 in LTS (730)	Week 104	549 to 913 days
Month 30 in LTS (1095)	Week 156	914 to 1278 days
Month 42 in LTS (1460)	Week 208	1279 to 1643 days
Month 54 in LTS (1825)	Week 260	1644 to 2008 days
Month 66 in LTS (2190)	Week 312	2009 to 2373 days
Month 72 in LTS (2372)	Week 338	2374 to 2402 days

*Study days are days since the first infusion in the TDR12857 study.

**For patients who enrolled in LTS13769, the upper boundary of the window is 176 days or (1st day of LTS – 1), whichever is earlier; for patients who didn't enroll in LTS13769, use study day 176 as cutoff.

Table 6 – Plasma concentration of avalglucosidase alfa

VISIT (target study day*)	Analysis Visit	Analysis Visit Window (in study days*)
Baseline	Baseline	
Week 1 in TDR (1)	Week 1	1 to 42 days
Week 13 in TDR (85)	Week 13	43 to 127 days
Week 25 in TDR (169)	Week 25	128 to 273 days/(1 st day of LTS – 1)**
Month 6 in LTS (365)	Week 52	(1 st day of LTS) to 548 days
Month 18 in LTS (730)	Week 104	549 to 913 days
Month 30 in LTS (1095)	Week 156	914 to 1278 days
Month 42 in LTS (1460)	Week 208	1279 to 1643 days
Month 54 in LTS (1825)	Week 260	1644 to 2008 days
Month 66 in LTS (2190)	Week 312	2009 to 2373 days
Month 72 in LTS (2372)	Week 338	2374 to 2402 days

*Study days are days since the first infusion in the TDR12857 study.

**For patients who enrolled in LTS13769, the upper boundary of the window is 273 days or (1st day of LTS – 1), whichever is earlier; for patients who didn't enroll in LTS13769, use study day 273 as cutoff.

Table 7 –MRI, muscle biopsy

VISIT (target study day*)	Analysis Visit	Analysis Visit Window (in study days*)
Baseline	Baseline	
Week 27 in TDR (184)	Week 27	92 to 273 days/(1 st day of LTS – 1)**
Month 24 in LTS (365)	Week 52	(1 st day of LTS) to 1278 days
Month 48 in LTS (1095)	Week 156	1279 to 2008 days
Month 72 in LTS (2372)	Week 338	2009 to 2402 days

*Study days are days since the first infusion in the TDR12857 study.

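### SAP Appendix B windows stop at day 2402, leaving the additional follow-up phase without analysis visits; in Tables 5 and 6 the Month 72 target falls in the Month 66 window

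*SAP*

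**What the plan says.** SAP Section 2 sets the scope: "The statistical analysis and reporting will be based on all data from study TDR12857 and its extension study, LTS13769". Appendix B assigns visit labels by study day, counted from the first TDR12857 infusion. Its method begins "The analysis visits are assigned by comparing the distance between the calculated study day of each assessment" and goes on to name the target days and windows. It adds: "All visits in the applicable datasets will be used, including scheduled and unscheduled visits". Where several values share a window, rule 1 says "the assessment performed closest to the target study day will be used in the by-visit analysis". On patients moved to 20 mg/kg within LTS13769 it says: "For change from TDR12857 baseline analyses, rebaseline visit and assessments performed after rebaseline will be handled in the same manner".

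All seven tables close with a Month 72 row (target day 2372) whose upper limit is day 2402. Table 1 gives that row "2282 to 2402 days". Tables 5 (Hex4) and 6 (plasma concentration) give it "2374 to 2402 days", directly after a Month 66 row (target 2190) of "2009 to 2373 days". The closing lines of the appendix send only two kinds of result to recorded visits: assessments absent from the tables, and changes from rebaseline.

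Under protocol 6.2.1 and 10.1.3, patients who finish six years enter an additional follow-up phase. It lasts until local approval, with a 2-year cap in the UK, Germany and Denmark. ECG, hematology, urinalysis, biochemistry, anti-avalglucosidase alfa antibodies, 6MWT and PFT continue every 6 months (10.1.3.4) and MRI every 2 years (10.1.3.6). Hex4 and, where required, biopsy are taken at the end-of-study visit (10.1.3.7).

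**The concern.** The windows appear to have been written for a six-year study. Amendment 06 (6 September 2019) added the follow-up flow chart, and the SAP was signed 202 days later, from 26 March 2020. The SAP still has no follow-up rows, and its Section 2.1.4 cites protocol Section 10.1.2.9, which is not in the current numbering.

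The primary objective includes long-term safety. The outputs that lose data are the by-visit laboratory and ECG changes from TDR12857 baseline, and the mean-change plots of ALT, AST, creatinine, CK and CK-MB (SAP 2.4.5.3). They would lack the longest-exposure values. Late MRI, biopsy and Hex4 values are lost in the same way; for LTS MRI the reference is the Week 27 LTS baseline. 6MWT and PFT changes with 95% CIs are also affected, but the protocol erratum makes those exploratory. With no rule for late values, they would be either left out or windowed after the open-label data had been seen.

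Separately, a window that excludes its own target mislabels a sample taken exactly on schedule.

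**Working it through.** **1. The rule most rows follow.** The upper limit is the midpoint of adjacent targets. In Table 1, Months 66 and 72: (2190 + 2372)/2 = 2281, as printed. The other LTS rows of Table 1 reproduce to within rounding. The last row has no successor and stops at 2372 + 30 = 2402.

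**2. Distance from the cut-off to the follow-up visits.** Six-monthly steps from day 2372 give days 2555, 2737, 2920 and 3102. The first is 2555 − 2402 = 153 days past the limit.

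**3. Share of follow-up with no window.** Assume LTS entry on day 183 (the target for LTS Day 1 in Table 4) and participation to the 8-year cap.
- Last day: 183 + 2920 − 1 = 3102.
- Days without a window: 3102 − 2402 = 700, and 700/2920 = 24.0%.
- Entry on day 274, the day after the latest Week 25 limit in Table 1: last day 274 + 2920 − 1 = 3193, so 791/2920 = 27.1%.
- Approval by year 6: 0 for entry on day 183. Month 72 is 2191.5 days after entry (72 × 365.25/12), so for entry after about day 210 (2402 − 2191.5 = 210.5) the Month 72 visit itself falls past the limit.
- Countries without the 2-year cap could exceed these shares.

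**4. The same loss counted in visits, with two years of follow-up.**

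| Assessments | LTS rows printed | Rows missing | Share |
|---|---|---|---|
| Table 1 items (6-monthly) | 12 | 4 | 4/16 = 25% |
| Table 3 antibodies (if 6-monthly) | 28 | 4 | 4/32 = 12.5% |
| Table 4 biochemistry | 49 | 4 | 4/53 = 7.5% |
| Table 7 MRI | 3 | 1 | 1/4 = 25% |

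**5. Tables 5 and 6 boundary.** Because 2009 ≤ 2372 ≤ 2373, the Month 72 target is in the Month 66 window and outside its own. The midpoint is 2281, not 2373. The printed figure fits a next yearly target: (2190 + 2555)/2 = 2372.5.
- Days 2282 to 2373 (92 days) are 92 to 183 days from 2190 but only 90 to 1 days from 2372.
- The Month 72 window is 29 days (2374 to 2402) instead of 121 (2282 to 2402).
- In a ±14-day visit around day 2372 (2358 to 2386), 16 of the 29 days are labelled Month 66.
- A Month 66 Hex4 on days 2176 to 2204 is at most 14 days from its target, so under rule 1 it displaces any end-of-study Hex4 on days 2282 to 2373.

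**6. Table 7 targets.** Months 24 and 48 have targets 365 and 1095 (Weeks 52 and 156), against 912 and 1642 (Weeks 130 and 234) in Table 1. The difference is 912 − 365 = 1642 − 1095 = 547 days. Target 1095 lies outside its own window (1279 to 2008). The printed limits, 1278 and 2008, match the midpoints from the Table 1 targets to within a day: (912 + 1642)/2 = 1277 and (1642 + 2372)/2 = 2007. The printed targets would give 730 and 1733.5.

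**The case against.** The statement that all visits are used can be read as describing which visit types enter the windowing. On that reading the cut-off is an omission after an amendment and not a contradiction. The reading is fair, but the result is the same: the affected assessments are listed in the tables, so the recorded-visit fallback does not reach them.

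Much of the safety evidence does not depend on windows. Listings, TEAE and PCSA counts, Kaplan-Meier liver analyses, peak ALT or AST against bilirubin plots, possible Hy's law listings, and peak and last antibody titers all keep late data. Vital signs and physical examination use recorded visits. For LTS-switch patients, rebaseline analyses of efficacy, laboratory, ECG and MRI also keep it. This stands: the loss is confined to by-visit change from the original (for LTS MRI, Week 27) baseline. Patients on 20 mg/kg from the start have no rebaseline to fall back on. Whether the spaghetti plots keep late values depends on their time axis, which SAP 2.4.4.2 does not state.

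The 24% is a calendar share at the cap; for biochemistry, 4 of 53 visits is nearer 8%. That also stands, and both figures are shown above.

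For LTS-switch patients, whose schedule restarts at the first 20 mg/kg infusion, yearly sampling puts about one routine Hex4 or PK sample in the 365-day Month 66 window. A sample on day 2300 would then be mislabelled but not dropped, and after the correction that patient's Month 66 cell could be empty. Displacement is therefore mainly a risk for end-of-study Hex4. The corrected label is still the nearer one: 72 days from target instead of 110.

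**Conclusion.** The point holds. Applied as written, Appendix B leaves follow-up values after day 2402 out of the windowed by-visit summaries. The share of LTS days without a window runs from 0 (approval by year 6) to 24% (8-year cap), assuming entry on day 183. Later entry raises both ends, and countries without the cap could go higher. Tables 2 and 6 lose little or nothing to the cut-off, because protocol 9.1.7 and 9.2.1 limit those samples to six years; in Table 5 the loss is end-of-study Hex4.

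The Month 66/72 boundary in Tables 5 and 6 is wrong by the SAP's own rule but minor alone. The Table 7 targets contradict both Table 1 and Table 7's own windows. The documents do not say how many patients any of these errors touches, and it may be none. The errors should be corrected before database lock; they do not threaten the study's conclusions.

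**What to change.** Keep the TDR12857 day count and amend Appendix B as follows.

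- **Tables 5 and 6:** Month 66 becomes 2009 to 2281; Month 72 starts at 2282. Add an end-of-study row to Table 5 for later Hex4.
- **Tables 1, 3 and 4:** extend Month 72 to 2463. Add Month 78 (target 2555) 2464 to 2646, Month 84 (2737) 2647 to 2828, Month 90 (2920) 2829 to 3011, and Month 96 (3102) from 3012. Continue with the same step and midpoint rule while any patient has data, and set no final upper limit.
- **Table 3:** first reconcile the 3-monthly antibody sampling in protocol 9.1.7 with the 6-monthly schedule in 10.1.3.4. If 3-monthly applies, Month 72 ends near (2372 + 2464)/2 = 2418 and the new rows are 3-monthly.
- **Table 7:** reconcile the Month 24 and 48 targets and week labels with Table 1; the printed windows fit 912 and 1642. Extend Month 72 to (2372 + 3102)/2 = 2737 and add Month 96 from 2738.
- **Tables 2 and 6:** add follow-up rows only if the end-of-study PK and anti-alglucosidase alfa IgG samples in the protocol's graphical design (1.1) are confirmed; Sections 1.2.3 and 10.1.3.7 omit them.
- **SAP 2.1.4:** replace the reference to protocol 10.1.2.9 with 10.1.3.8.

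The cost is table edits and some reprogramming of visit assignment, with no change to data collection. Late rows will be small, so show n beside each estimate.

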**For patients who enrolled in LTS13769, the upper boundary of the window is 273 days or (1st day of LTS – 1), whichever is earlier; for patients who didn't enroll in LTS13769, use study day 273 as cutoff.

Other assessments not specified above, if presented in by-visit summary tables, will use the recorded visits, rather than defined analysis visits.

By visit analyses of changes over time from rebaseline will use the rebased visits recorded.

Signature Page for
lts13769-16-1-9-sap

Approve & eSign	[Name] Clinical 26-Mar-2020 21:03:03 GMT+0000
-----------------	---

Approve & eSign	[Name] Clinical 27-Mar-2020 18:21:06 GMT+0000
-----------------	---

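### SAP Appendix B, Table 7 labels the LTS Month 24 and Month 48 MRI and biopsy results 78 weeks too early

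*SAP*

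**What the plan says.** Appendix B of the SAP assigns each assessment to an analysis visit by comparing its study day with a target day and a window. All tables count study days from the first TDR12857 infusion.

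- Table 7 (MRI, muscle biopsy) prints "Month 24 in LTS (365" with label Week 52 and a window ending on day 1278. It then prints "Month 48 in LTS (1095" with label Week 156 and window "1279 to 2008 days". Month 72 is day 2372, Week 338.
- Tables 1 to 4 print "Month 24 in LTS (912" with label Week 130, and "Month 48 in LTS (1642" with label Week 234.
- When several values share a window, general rule 1 says that "the assessment performed closest to the target study day will be used in the by-visit analysis". On equal distance, rule 3 takes the later date.
- For change from the TDR12857 baseline, "rebaseline visit and assessments performed after rebaseline will be handled in the same manner". By contrast, "By visit analyses of changes over time from rebaseline will use the rebased visits recorded".

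Protocol section 10.1.2.6 schedules MRI and biopsy every two years. For patients switched to 20 mg/kg, the flow chart in section 1.2.2 (footnote e) counts the schedule from their first 20 mg/kg infusion in LTS13769.

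**The concern.** The same visit cannot fall on two different days of one scale. The target and the week label in both Table 7 rows match visits 18 months earlier, and the Month 48 target does not lie inside its own window.

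MRI and biopsy remain secondary pharmacodynamic endpoints after the protocol erratum, and the secondary objective still includes the time course of response. The week label is the time axis a reader sees, so a result from about two and a half years of treatment would be presented as a one-year result. The target day also decides which value is analysed when a window holds more than one.

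**Working it through.** **1. Which visit do days 365 and 1095 belong to?** Table 4 places LTS Day 1 at study day 183. Expected day = 183 + months × 365.25/12.

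| LTS visit | Expected day | Tables 1–4 | Table 7 |
|---|---|---|---|
| Month 6 | 365.6 | 365 / Week 52 | – |
| Month 24 | 913.5 | 912 / Week 130 | 365 / Week 52 |
| Month 30 | 1096.1 | 1095 / Week 156 | – |
| Month 48 | 1644.0 | 1642 / Week 234 | 1095 / Week 156 |
| Month 72 | 2374.5 | 2372 / Week 338 | 2372 / Week 338 |

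The formula reproduces the SAP's own targets to within 3 days everywhere except the two Table 7 rows. Tables 5 and 6 also give day 365 / Week 52 to Month 6 and day 1095 / Week 156 to Month 30.

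**2. Size of the shift.** 912 − 365 = 547 days and 1642 − 1095 = 547 days. 130 − 52 = 78 weeks and 234 − 156 = 78 weeks.

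**3. Are the windows wrong too?** Midpoints between adjacent targets:

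- Printed targets: (365 + 1095)/2 = 730 and (1095 + 2372)/2 = 1733.5.
- Corrected targets: (912 + 1642)/2 = 1277 and (1642 + 2372)/2 = 2007.

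The printed upper bounds are 1278 and 2008, which fit the corrected targets to within 1 day. Day 1095 lies outside 1279–2008; day 1642 lies inside it. Only the targets and week labels of two rows are wrong.

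**4. Effect on the displayed time course.** With Week 27 as the LTS baseline for MRI, the printed labels 27, 52, 156, 338 give gaps of 25, 104 and 182 weeks. The corrected labels 27, 130, 234, 338 give 103, 104 and 104. If nominal week were used as time, a constant rate of change would look too fast at the two visits by:

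- MRI, from Week 27: 103/25 = 4.1 and 207/129 = 1.6.
- Biopsy, from the TDR12857 baseline: 130/52 = 2.5 and 234/156 = 1.5.

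**5. Effect on which scan is analysed.** Take scans at days 912, 1642 and 2372 before any switch, then one at re-baseline (day R) and every 730 days after, ignoring the ±14-day tolerance and early end-of-study scans. Apply rules 1 and 3.

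- For R from 184 to 547, both R and R + 730 (at most 1277) fall in the Month 24 window. Target 365 always picks R. Target 912 picks R + 730, because R − 182 is at most 912 − R; at R = 547 both distances are 365 and the later date wins.
- Example, R = 400: scans on days 400 and 1130. Target 365 picks day 400 (35 days away against 765). Target 912 picks day 1130 (218 against 512).
- At R = 548 both targets pick R, and from R = 549 the next scan leaves the window. On this schedule the selection never changes from day 548 on, and never in the Month 48 row.
- Protocol section 10.1.2.7 lets an MRI or biopsy from the previous 6 months serve as re-baseline. If the Week 27 scan (target day 184) is reused within 183 days, no new scan is taken up to day 367, and the range shrinks to about days 368–547.

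**The case against.** The strongest reply is that the damage is small. With one scan per window, the means, SDs and changes from baseline are unchanged. The visit column of Table 7 still names Months 24 and 48, so a careful programmer may spot the error. SAP section 2.4.7 plans descriptive summaries by visit and specifies no MRI or biopsy plot over time. The longitudinal model is optional twice over: it depends on an observed linear trend and even then only may be used. No time variable is stated, and actual study day is available. All of this stands, so the multipliers in step 4 are conditional and do not describe a planned output.

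The selection effect may also be empty. The re-baseline visit came in with Amendment 03, dated 29 January 2016. If nobody was re-baselined before that date, re-baseline by day 547 requires a first TDR12857 infusion on or after 31 July 2014, and re-baseline on day 368 requires 26 January 2015 or later. The documents give no enrolment dates. Biopsy is narrower still, because it is waived when prior glycogen was below 5% without significant clinical decline.

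Early end-of-study scans do not help the other way for patients who never switched. At nominal timing, such a scan sharing a window with the day 912 or day 1642 scan is later than it, so both the printed and the corrected target keep the scheduled one. For an LTS-switch patient the choice can change. As an illustration, re-baseline on day 600 gives a next scan on day 1330. An end-of-study scan on day 1700 would share the Month 48 window: target 1095 picks day 1330 (235 days against 605), target 1642 picks day 1700 (58 against 312).

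Finally, the bounds 1278 and 2008 also appear in Tables 5 and 6 between other visits, so the midpoint match alone does not identify the right targets. The correction rests mainly on Tables 1 to 4 and the two-yearly schedule, and the midpoints agree with it.

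None of this removes the labelling error, which needs no unusual patient.

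**Conclusion.** The concern holds and should be fixed. The certain effect is that every Month 24 and Month 48 MRI or biopsy result analysed by Table 7 carries a week label 78 weeks too early. Distorted rates of change follow only if nominal week is used as time. A changed scan selection requires two or more scans in one window: on the protocol schedule, that means an LTS-switch patient re-baselined on days 184–547, in the Month 24 row only. Otherwise it needs an unscheduled or early end-of-study scan. The number of such patients or scans is unknown. Changes from rebaseline are unaffected.

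**What to change.** In Appendix B, Table 7, set the Month 24 row to day 912 / Week 130 and the Month 48 row to day 1642 / Week 234. Keep the printed windows and the Month 72 row. If MRI or biopsy outputs already exist, check their visit labels and, for windows holding more than one value, which one was selected. The cost is four table cells and that check; no new data are needed.
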